The primary analyses will use an intent-to-treat approach and analyze all subjects according to randomized group. For subjects missing month 9 or 18 endpoints, these will be multiply imputed from the lower (worse) half of the distribution from their arm (conservative approach). Additional analyses will be conducted using a per protocol approach that includes only those subjects who complete the full intervention. Analyses will use women's data only; however, men's data will be used to validate outcomes a) increased contraceptive use, and b) reduced unintended pregnancy. Exploratory analyses using outcomes of contraception by type (e.g., LARC) may be conducted if numbers are sufficient across time-points.

At 18 month follow-up, healthcare facilities in the study area will be surveyed to assess provision of FP counseling and methods, availability of FP methods, approximate FP method client volume, provider type/qualifications, and participation in the CHARM2 intervention. Healthcare facility location GPS will be collected for mapping of healthcare services in the study area; no personally identifying information regarding the providers will be collected.

At 18 month follow-up, participants' location data will be re-collected in the form of GPS coordinates; this data will be used to examine distances to healthcare facilities in the study area. GPS data will be collected in a separate survey form to be accessed only by NIRRH in-country study staff. In-country study staff may use this location data, in conjunction with healthcare facility location data, to calculate participant-level distance to healthcare providers. Geolocation data will **not** be shared with UCSD or any other external sources; any maps produced which visualize healthcare facility location and access will **not** include participant locations. Calculated distances **only** may be shared with UCSD analysts, to be summarized and utilized in adjusted regression models to better understand drivers of and barriers to health care services generally, and family planning services specifically, in the study area.

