## **Qualitative Data Collection:**

In-depth interviews with CHARM2 providers and participants, as well as control condition couples, described as part of Aim 3, will assess perceived outcomes of the intervention, for triangulation with quantitative findings.

At 9 month follow-up, a subsample of CHARM2 couples (n=50 couples; 5 per CHARM2 intervention cluster) will be randomly selected to participate in IDI to assess how the program altered their relationship and behaviors, including FP, MSV and sexual communication. Interviews will be 45-60 minutes in length and conducted in Marathi. Interview participation may influence responses at 18 month follow-up but delaying qualitative feedback to 18 month follow-up may affect participant recall. Thus, we will compare these individuals at 18 month follow-up with those intervention participants who did not participate in interviews, and if significant differences are seen, we will drop them from further analyses. MILs of couples (mother's of the young married men) that participate in IDIs will also be invited for interviews *only* through the couples themselves, and with the couples knowledge that we will be describing the CHARM2 intervention to them. FGDs with MILs will assess family dynamics of young couples with regard to husband's parents, family planning attitudes, and their perceptions of the CHARM2 program.

All CHARM2 providers (n=20 providers/ANMs/counselors) will be asked to participate in IDIs to assess their perceptions of CHARM2 quality, acceptability and utility. NIRRH staff will conduct the 30 minute open-ended interviews with providers. As is standard in India, no monetary incentives will be offered.

At 18 month follow-up, a subsample of control condition couples (n=20 couples, 2 per control cluster) will be randomly selected to participate in IDI to understand FP counseling and access and gender-based violence in the study area outside of the CHARM2 intervention.

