**Data Analysis:** The primary comparison of the binary outcomes between intervention groups at 9 & 18-months will use mixed-effects longitudinal logistic regression, with random effects for the individual (couple) and for geographical clusters, over time. Baseline will be included as a time point (Aims 2a, 2b only). A categorical time effect will be used (profile model). A “difference-in-differences” analysis will compare the treatment arms. Statistically, this amounts to testing for an interaction between time and treatment arm in the longitudinal model. In addition, the intervention groups will be compared via a generalized estimating equations (GEE) logistic regression analysis. The GEE models will use a nested exchangeable working correlation matrix that takes into account geographic clusters and the individual (couple) within the cluster. No other covariates will be included in the primary analysis. Since the treatment assignment is at random this “un- adjusted” analysis will provide a causal effect of the intervention. However, we will also conduct secondary analyses, adjusting for potentially relevant covariates (e.g., age, current pregnancy, past year child- birth, etc.), in addition to time and treatment arm, using backward model selection at the  $\alpha=0.15$  threshold level. These secondary analyses may improve precision (power) of estimating the treatment effect and reduce any bias due to random imbalances between arms.

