- a) Based on CHARM, we expect the proportion of women using modern contraception in the control group to be 40% at 18 month follow-up. This study will have 83.3% power to detect an absolute difference of 12% or more between treatment groups at follow-up, or 40% vs 52% in the two groups, with total kappa [variance]=0.10, assumed to be split equally between within-village variance and within-cluster variance . These values were found in the CHARM study.
- b) Based on CHARM, we expect that 89.2% of women in the control group will report no recent MSV at 18 month follow-up. We have 91.5% power to detect an absolute difference of 6% or more between treatment groups (89.2% vs. 95.2%) with kappa=0.036,

assumed to be split equally between within-village variance and within-cluster variance. The effect size of 6% difference and the kappa=0.036 were observed in the CHARM study.

c) Based on CHARM, we expect the proportion of women with no unintended pregnancy over 18 month follow-up to be 90% in the control group. This study will have 89.5% power to detect an absolute difference of 5.5% or more between groups (90% vs. 95.5%), with kappa=0. The effect size of 5.5% difference is based on a meta-analysis of cluster RCTs evaluating impact of FP interventions on unintended pregnancy (with comparable measures to this study). The study showed a 50% reduced risk for intervention participants with no unintended pregnancy in the CHARM group, or 5.5%. The kappa=0 is based on the CHARM study, where no significant intra-cluster correlation was found for this outcome.

While we will use longitudinal mixed effects logistic regression methods in our analyses, for power calculations we considered only the 18-month time point in a model similar to those to be used in the analyses. Power for the prescribed longitudinal analyses will be higher. Power calculations for each hypothesis used statistical simulations with 10,000 iterations. The conversion from kappa to the random cluster effect was done using the delta method, and was confirmed through the simulation.

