## **12. INFORMED CONSENT**

Recruitment and written consent (hard copy) will be implemented by trained Masters-level research staff for all phases of study; research staff and participants will be gender-matched. For every source of primary data collection, written informed consent will be acquired prior to data collection. For RCT study participants, consent will be obtained prior to screening, survey, and, for women, urine pregnancy testing; consent will include follow-up data collection. For IDI participants, written informed consent will again be provided prior to interviews; all IDIs are 1-time events. Stakeholders providing IDI (Aim 3) will provide verbal informed consent prior to participation; verbal consent will be used to facilitate use of phone interviews since no personal questions will be included in these interviews.

It must be noted that issues of literacy are a major concern in rural India, particularly for women. [name] and other Co-Is on this study have years of experience obtaining written informed consent with both illiterate and literate men and women in rural India. In the case of illiterate men/women, the consent form will be read in the presence of a trusted literate adult (18 years or older) of the participant's choosing, and then the individual will be asked in the presence of that adult whether they are willing to participate. Research staff will provide explanations to all queries, and anything that cannot be answered in the field will be addressed via telephone contact with [name].

The consent forms and survey forms will be prepared in Marathi language. Written consent will be required, as our in-country research partner NIRRH prefers written informed consent, rather than verbal consent, in behavioral studies involving sensitive research questions, such as those used in the current study. Although females aged 18-21 years will likely be included in this study, parental consent for their participation will not be obtained, as all of these females will be wives and are thus recognized as adults capable of providing consent for themselves in the Indian context.

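### Interviewed CHARM2 couples are dropped if their 18-month results differ significantly: an outcome-dependent, one-arm exclusion that conflicts with intention-to-treat and has no stated test, alpha, outcome or direction

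*Combined protocol and SAP*

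**What the plan says.** Section 9, Qualitative Data Collection, states that at the 9-month follow-up "a subsample of CHARM2 couples (n=50 couples; 5 per CHARM2 intervention cluster) will be randomly selected to participate in IDI". It accepts that being interviewed may affect later answers, and so "we will compare these individuals at 18 month follow-up with those intervention participants who did not participate in interviews"; "if significant differences are seen, we will drop them from further analyses". Another 20 control couples are interviewed, but at 18 months, with no comparison and no drop rule.

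Section 9, Quantitative Data Collection, sets the analysis population: "The primary analyses will use an intent-to-treat approach and analyze all subjects according to randomized group". It makes no exception for interviewed couples. The only restricted set it defines is per protocol, based on completing the intervention. Under Data Analysis, the primary model is a "mixed-effects longitudinal logistic regression, with random effects for the individual (couple) and for geographical clusters", again with no mention of the exclusion.

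Section 12 makes interview consent a separate step: "For IDI participants, written informed consent will again be provided prior to interviews".

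**The concern.** The rule removes randomised couples from one arm because of their own 18-month data. The phrase on further analyses is not defined. However, the trigger needs data from the last follow-up, and the Timeline puts the 18-month visit at month 22 and the outcome analysis at month 40. Nothing confines the exclusion to secondary work, so it meets the intention-to-treat statement head on and the two passages must be reconciled.

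The rule is also incomplete. It does not say which outcome is compared, by what test, at what level, in which direction or with what allowance for clustering. It does not say whether dropped couples would then count as missing and be imputed. Someone holding the 18-month data could settle all of this afterwards.

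The comparison group is those who did not take part in an interview, not those who were not selected. Because consent to the interview is separate, a difference could reflect who agreed and not any effect of the interview.

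**Working it through.** **Inputs.** From Section 9: 50 interviewed couples (5 in each of 10 CHARM2 clusters); 600 couples per arm; 80% retention, so 480 observed per arm. Planned event rates at 18 months, from Sample size considerations:
- marital sexual violence (MSV): 10.8% control, 4.8% CHARM2
- unintended pregnancy: 10% control, 4.5% CHARM2
- modern contraception: 40% control, 52% CHARM2

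**Assumptions.** Two-sided 0.05 for the trigger (none is stated); no true interview effect unless noted; clustering ignored. Either 40 interviewed couples against 440 others are observed (80% retention) or 50 against 430 (all interviewed couples retained, since they were seen at month 9).

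**The plan's own figures.** 5 × 10 = 50, which is 50/600 = 8.3% of the CHARM2 arm and 0% of control. For unintended pregnancy (kappa = 0) the pooled two-proportion formula with 480 per arm gives a null standard error of √(2 × 0.9275 × 0.0725/480) = 0.01674 and an alternative standard error of √((0.90 × 0.10 + 0.955 × 0.045)/480) = 0.01664. Power is Φ((0.055 − 1.96 × 0.01674)/0.01664) = 90.9%, close to the stated 89.5% from simulation. With 40 observed CHARM2 couples dropped (440 against 480), the same formula gives 89.5%. The loss of power is therefore only about 1 point.

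**How often the rule fires, and which way.** The probabilities of all pairs of event counts (interviewed, other) were enumerated exactly from two binomials with the same true rate. A firing favours CHARM2 when the dropped group did worse than the rest. Ranges cover both follow-up assumptions and, where pooled, both outcomes.

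| Outcome and true rate | Test | Fires | Firings favouring CHARM2 | Mean bias over all trials (points) |
|---|---|---|---|---|
| MSV 4.8%, pregnancy 4.5% | Pearson | 3.7–3.9% | 96–99.9% | about +0.03 |
| Same | Likelihood-ratio | 7.6–8.8% | 26–30% | −0.015 to −0.007 |
| MSV 10.8%, pregnancy 10% | Pearson | 4.6–4.7% | 69–72% | about +0.02 |
| Same | Likelihood-ratio | 5.4–5.6% | 42–44% | about 0 |
| Contraception 52% | Pearson | 4.9–5.0% | about 51% | about 0 |

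The reversal comes from zero counts. At 4.8%, no events among 40 couples has probability 0.952^40 = 14%. For 0/40 against 22/440 the Pearson statistic is 0.05²/(0.04583 × 0.95417 × (1/40 + 1/440)) = 2.10, below the critical value of 3.84. The likelihood-ratio statistic for the same table is 2 × [22 ln(22/20.17) + 40 ln(40/38.17) + 418 ln(418/419.83)] = 3.92, above it. One test keeps a better-than-average group and the other drops it.

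**Any of three outcomes, if independent.** Pearson at planned rates, 40 against 440: 1 − 0.9613 × 0.9614 × 0.9508 = 12.1%; at control-level rates, 13.6% to 13.7%. Likelihood-ratio at planned rates: 20% to 21%.

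**Shift when it fires.** Dropping n interviewed couples of 480 moves the arm rate by (n/480) × (gap between the groups). For contraception the smallest significant gap is 1.96 × √(0.52 × 0.48 × (1/40 + 1/440)) = 16.2 points, or 14.6 points for 50 against 430. The shift is therefore at least 16.2 × 40/480 = 1.3 or 14.6 × 50/480 = 1.5 points, and averages 1.6 to 1.8, against a planned effect of 12. For MSV or pregnancy it averages 0.7 to 1.2 points (Pearson, firings that favour CHARM2), against planned effects of 6.0 and 5.5.

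**False positives.** In 2,000,000 simulated trials per setting, with 480 per arm, a simple two-proportion test, control-level rates and a Pearson rule on the one outcome, the one-sided rate rises from 2.5% to about 2.6% to 2.7%.

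**Does it catch a real interview effect?** For a true 10-point effect on contraception (62% or 42% against 52%) the trigger has 22% to 27% power.

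**The case against.** Four points deserve weight.

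- The text never says that further analyses include the primary one, and it speaks of responses at 18 months without naming a trial endpoint. Both readings are inferences. This stands as a caveat, but the wording and the Timeline point that way and nothing in the plan says otherwise. If something narrower was meant, the plan must say so.
- The one-arm check has a reason. CHARM2 interviews come nine months before the endpoint, whereas control interviews take place at the 18-month visit, so only CHARM2 couples carry an earlier interview into their 18-month answers. That explains why the comparison is made in one arm. It does not justify deciding on exclusion from those couples' outcomes.
- Interviewees are randomly selected, so removing them is roughly unbiased. That is true of unconditional removal by selection. It is not true once removal depends on their results, or if the group is defined by who agreed to be interviewed. No refusal rate is given, so the size of the consent problem is unknown.
- The average harm is very small, and the tests examined are not in the plan. Both statements are correct. The figures ignore clustering and baseline, and the any-of-three figure assumes independence although contraception and pregnancy are plausibly related. What survives is that the plan's silence lets the choice of test decide which way the exclusion leans.

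**Conclusion.** The concern holds. The plan contains an operative, outcome-dependent exclusion that can touch only CHARM2 couples, is not specified well enough to apply, and conflicts with the intention-to-treat statement on its natural reading. The numerical effect is modest: mean bias of at most about 0.03 points, a one-sided error near 2.6% to 2.7% instead of 2.5%, and about 1 point of power. In the trials where it fires, the CHARM2 rate moves by roughly 0.7 to 1.8 points, in a direction that depends on an unstated choice, and the primary result is no longer intention-to-treat and is open to challenge. The rule would also miss a 10-point interview effect about three times in four. These figures rest on a two-sided 0.05 trigger, 40 or 50 interviewed couples observed, and independent couples. The missing specification does not depend on any of them. This should be corrected, chiefly to protect the integrity of the primary analysis set.

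**What to change.** Delete the test-then-drop sentence and state that all interviewed couples stay in the intention-to-treat primary analysis. Pre-specify one sensitivity analysis with the primary model, run whatever the comparison shows, that excludes every CHARM2 couple randomly selected for interview. Define the group by selection, not by completing the interview. Report it beside the primary result, with the share of missing endpoints in each arm.

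The cost is one wording change and one extra model run. There are two downsides:
- A real interview effect stays in the primary estimate, though diluted: a 10-point effect moves the arm rate by 10 × 40/480 = 0.8 to 10 × 50/480 = 1.0 points.
- In the sensitivity analysis, if all 50 selected couples are observed at 18 months, the CHARM2 missing share rises from 120/600 = 20.0% to 120/550 = 21.8%. With the planned imputation from the worse half of the arm, that works slightly against CHARM2. If 40 of the 50 are observed, the share stays at 110/550 = 20.0%.

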## **Quantitative Data Collection:**

Survey and urine pregnancy test data (from wives) will be collected from all enrolled couples in the CHARM2 RCT evaluation study. Both intervention and SOC arm participants will provide survey data at baseline and 9 & 18 month follow-ups. Survey data will be collected electronically on tablets using a unique identifier to link data between couples and across time. Wives in both the intervention and the SOC arms will be tested for pregnancy using a urine specimen at baseline and at both post-test timepoints; these data will directly be entered into the password protected electronic survey system at the time of survey data collection. Urine samples for pregnancy testing will not be retained for the study, but will be disposed of in disposal facilities upon completion of the test. Survey and pregnancy test results data will be stored locally on the tablet and, when internet is available, uploaded to the password-protected server. Separately, a list of contact names with unique identifiers will be maintained for tracking purposes; a hard copy form of this list will be kept in a locked file in [name] locked office at NIRRH. Baseline and follow-up surveys will be collected from couples using measures from the original CHARM study, which was based on India's Demographic and Health Survey (DHS/India's NFHS-3) and other validated measures. Couples must meet the eligibility criteria outlined below.

Eligible couples will be:

- Young wives (aged 18-29 years) and their husbands
- couples fluent in Marathi and both willing to participate
- no sterilization or infertility indicated (infertility is defined as having no pregnancy for 1+ years despite non-use of traditional or modern contraception)
- no pregnancy or female/male surgical sterilization planned for the next 18 months, and no reported use of consistent use of modern contraceptives in the past three months, and
- residing in the village for at least 2 years and residing together for at least 3 months, to facilitate follow-up tracking

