## 11. RECRUITMENT

This study involves randomization at the geographic cluster rather than individual level. While individual randomization is more powerful, cluster randomization allows us to reduce risk for contamination that may occur if both treatment conditions were offered in the same geographic area. Participating couples will be recruited from geographic clusters of approximately equal size mapped for randomization. Clusters are geographically distinct areas with administrative boundaries, natural borders and appropriate distance from other study clusters to reduce risk for contamination. Clusters will be created based on geographic boundaries, population density (approximately 5000 population per cluster), and proximity to ANMs and health providers. Clusters will be selected based on minimum number of eligible couples (at least 60 eligible couples); clusters will then subsequently be randomized to intervention or control conditions using computer-generated random numbers. Households within each cluster will be screened sequentially for eligibility. Research staff are not to be blinded to the treatment condition assignment to clusters. Recruitment of eligible households will be n = 60 per cluster. In a small cluster if the total number of eligible couples is equal to 60, all couples are approached for recruitment. In a larger cluster if the eligible couple number is more than 60, the required number of couples will be selected through systematic random sampling (selecting every nth participant).

Trained NIRRH survey research teams (1 male & 1 female) will approach selected households for screening and recruitment. Three attempts to reach the couple will be made for each selected household. If an eligible household has two or more couples meeting eligibility criteria, a Kish Grid will be used to determine the participants. Couples selected from eligible households will be asked to join the study and will be informed that the study focuses on FP. Data will be collected to assess participation rates and biases by

age, and contraceptive use. Recruitment/enrollment and intervention delivery will occur over 2.5 years on a rolling basis.

**PLEASE NOTE:** No identifiable information will be collected from those screened and found to be ineligible or unwilling to participate, across study phases.

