### **Importance of the Knowledge to be Gained**

Data collected from this project will be used to create program efforts that can be integrated into national rural health and family planning policies and initiatives, with the goal of improving family planning and reducing unintended pregnancy at a population level.

**Interim Safety and Efficacy Review.** Study risks are low. However, we will convene a Data and Safety Monitoring Board (DSMB) to review safety on a yearly basis. The study will be stopped early if there are serious safety concerns or early evidence of a large beneficial treatment effect. An interim efficacy analysis will be conducted after half of subjects (n=10 geographical clusters) have completed the 18 month visit. The O'Brien-Fleming stopping rule for efficacy will be used. Because validation of the proposed CHARM2 intervention is scientifically important independent of statistically significant results, there will be no futility analysis. The DSMB will consist of experts on FP, MSV and clinical trials in India.

**Confidentiality and Security.** Data security and confidentiality are critically important due to the sensitive subject matter of this study. All participant identifiers such as name, address or telephone number will be maintained on separate forms in locked storage at NIRRH and kept separately from the analytic database. Data shared among NIRRH, Population Council, and UCSD will be maintained on password-protected and secure servers at each site. The data will be backed up nightly on the UCSD server.

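### The plan states no small-sample method for 20 clusters (10 at the interim) and does not settle whether the primary mixed model lets cluster effects change over time

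*Combined protocol and SAP*

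**What the plan says.** Section 9, Data Analysis, sets the primary analysis: "The primary comparison of the binary outcomes between intervention groups at 9 & 18-months will use mixed-effects longitudinal logistic regression". The arms are compared by difference-in-differences: "Statistically, this amounts to testing for an interaction between time and treatment arm in the longitudinal model". The model's random structure is given only as "with random effects for the individual (couple) and for geographical clusters, over time". The plan limits use of the baseline measurement to two of the three outcomes: "Baseline will be included as a time point (Aims 2a, 2b only"). A second analysis is a logistic GEE: "The GEE models will use a nested exchangeable working correlation matrix that takes into account geographic clusters and the individual (couple) within the cluster".

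Section 15, Interim Safety and Efficacy Review, adds: "An interim efficacy analysis will be conducted after half of subjects (n=10 geographical clusters) have completed the 18 month visit". It names the O'Brien-Fleming rule but not the model, outcome, alpha or sidedness.

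Section 6 has 20 clusters in total. Section 9, Qualitative Data Collection, implies 10 per arm: 50 couples at 5 per intervention cluster, and 20 couples at 2 per control cluster. No section states a degrees-of-freedom method, a bias-corrected variance, a t or F reference, or an explicit cluster-by-time random effect. The words about clusters over time can be read either way.

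**The concern.** Two gaps are separate and need separate remedies.

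- **Few clusters.** An ordinary cluster sandwich is biased downward with 10 clusters per arm, and a normal reference ignores that the variance is estimated on 18 df (8 at a balanced interim). If the GEE is run that way, its intervals are too narrow.
- **Random-effects structure.** In a difference-in-differences test a constant cluster effect cancels. If cluster effects shift between baseline and month 18 and the model has only a constant cluster intercept, the shift is not counted in the standard error.

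There is a trial-specific reason to doubt constancy for contraceptive use. Eligibility (section 9, Quantitative Data Collection) requires "no reported use of consistent use of modern contraceptives in the past three months". That compresses cluster differences in use at baseline and lets them open up later.

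At stake are the error rate of the main efficacy claims and the reproducibility of an early-stopping decision. With model, df and contrast left open, two competent analysts could reach different decisions from the same interim data.

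**Working it through.** **Inputs from the documents.** 10 clusters per arm; 48 analysable couples per cluster; follow-up contraceptive use 40% v 52% with kappa 0.10; no MSV 89.2% v 95.2% with kappa 0.036; no unintended pregnancy 90% v 95.5% with kappa 0. Kappa is split equally between village and cluster.

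**Assumed.** Two-sided 5%; boundaries 2.797 and 1.977 (nominal interim level 0.52%); 5 clusters per arm at the interim; kappa as a logit-scale variance; 4 villages per cluster unless varied. The planned imputation of missing endpoints was not modelled.

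**1. The plan's power figures (month 18 only).** For Aim 2a, the variance of a cluster proportion is p(1-p)/48 + [p(1-p)]² × (0.05 + 0.05/4).
- Control: 0.0050 + 0.0036 = 0.0086. Intervention: 0.0052 + 0.0039 = 0.0091.
- SE = sqrt((0.0086 + 0.0091)/10) = 0.042. Power = Φ(0.12/0.042 - 1.96), about 81%.
- With 4 to 48 villages the range is 81.4-84.4%, against 83.3% stated.

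Aim 2b gives 90.5-92.1% (1 to 48 villages), against 91.5% stated. Aim 2c gives 90.9% by two proportions with 480 per arm, against 89.5% stated. The logit-variance reading therefore fits.

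**2. Uncorrected GEE, closed form.** With K equal clusters per arm, the sandwich variance is (K-1)/K of the unbiased one, on 2K-2 df.
- Final, one contrast: 2P(t18 > 1.96 × sqrt(0.9)) = 7.9%.
- Interim boundary: 2P(t8 > 2.797 × sqrt(0.8)) = 3.7%; 3.7/0.52 is about 7.
- Joint test of both follow-ups, final: P(F(2,17) > 5.99 × 0.9 × 17/36) = 10.8%. Interim: P(F(2,7) > 10.52 × 0.8 × 7/16) = 8.1%.

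Simulation agrees for the single contrast (7.6-8.2% at cluster variance 0.10 or kappa 0.10). These figures depend on the number of clusters, not on an assumed autocorrelation.

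**3. Primary mixed model, no cluster-by-time term.** Simulated null error of the month-18 time-by-arm contrast, Wald z, contraceptive use. Set A: couple variance 1, kappa 0.10 split between cluster and village. Set B: couple variance 2, cluster variance 0.10.

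| Cluster effects over time | Set A | Set B |
|---|---|---|
| Constant | 5.2% | 4.9% |
| Correlation 0.8 | – | 6.2-7.5% |
| Correlation 0.5 | 7.9% | 8.1-9.9% |
| No cluster differences at baseline (use 10%) | 7.2% | – |
| Baseline and follow-up unrelated | 9.6% | – |

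Raising the cluster variance to 0.40 gives 9.8% at correlation 0.8 and 15.6% at 0.5. MSV moves only from 5.7% (constant) to 6.2% (0.5). For Aim 2c, with kappa 0, the month-18 mixed model gives 4.2%.

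At the interim boundary, set A gives 0.46% with constant effects and 1.2% at correlation 0.5, which is 0.9 and 2.3 times nominal.

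Using t(18) without the extra term still leaves 6.0% (correlation 0.5), 5.4% (no baseline differences) and 7.5% (unrelated). A df correction alone is not enough.

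**4. After correction.**
- Mixed model with cluster-by-time effect and 18 df, in the order constant, 0.5, no baseline differences, unrelated: 3.5%, 4.3%, 4.0%, 5.6%.
- GEE with Kauermann-Carroll sandwich and t(18), or F(2,17) if joint: 4.9-5.2%. With t(8) at the interim: 0.46-0.56% there and 4.9-5.3% over both looks.

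**5. Power of the planned contrast.** Corrected GEE with t(18), month-18 time-by-arm contrast, Aim 2a: about 67% (baseline use 20%, constant effects), 59% (20%, correlation 0.5), 48% (baseline use 10%). With no baseline cluster variation it is about 43%. MSV: 76%. The loss against uncorrected z is about 7-9 points. Mixed-model power for this contrast was not simulated.

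**6. Interim balance.** Section 11 says: "Recruitment/enrollment and intervention delivery will occur over 2.5 years on a rolling basis". If completion order is unrelated to arm, a 5:5 split has probability C(10,5)²/C(20,10) = 34%, 4:6 has 48%, and a worse split 18%. The corrected GEE with t(8) then gives 0.56-0.61% at 4:6 and 1.1-1.2% at 3:7.

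**The case against.** The GEE is additional, and the primary interaction test is sound if cluster effects are constant. The phrase about clusters over time may already mean time-varying effects. The eligibility rule removes only consistent users, so clusters may still differ at baseline. Autocorrelation, couple variance, baseline use and villages per cluster are all assumed, and the imputation was not simulated. A DSMB with clinical-trial expertise would probably look to the primary model.

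Most of this stands, and it limits three stronger readings that a reader might infer.

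- **That the primary test runs at 8%.** That figure belongs to the uncorrected GEE. The primary test's error is conditional and can be given only as a range.
- **That the stopping boundary will be crossed 7 times too often.** Section 15 names no model. The figure applies only if an uncorrected GEE with normal critical values governs stopping.
- **That the stated power shows a normal reference was used.** For Aim 2a, simulation gives 83.7% with z and 80.2% with t(18), against 83.3% stated. For Aim 2c it gives 91.4% and 88.9%, against 89.5%, which is nearer t(18). The two aims point in opposite directions, so nothing follows.

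The objection does not remove the gap. Nothing in the documents says a correction would be made or which reading of the random effects is meant, and the power calculation used month 18 alone, so it never tested the interaction.

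**Conclusion.** The omission is certain. For the additional GEE run uncorrected, the size is well established: about 8% for one contrast and about 11% for a joint test, given two-sided 5% and 10 clusters per arm. For the primary test of contraceptive use, error is about 5% with constant cluster effects. It is roughly 6-10% under moderate departures if the cluster-by-time term is left out, and higher in extreme cases. MSV is affected little. Unintended pregnancy is not inflated in the mixed model under the plan's own kappa of 0.

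The sample-size section's assurance that the longitudinal analyses will have more power than the month-18 calculation should not be relied on: the corrected-GEE runs for the time-by-arm contrast fall below 80% for both outcomes with a baseline. This should be settled before outcome data are seen. Confidence is medium, because the primary-model figures rest on inputs the documents do not give.

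**What to change.** 1. **Primary model, Aims 2a and 2b.** State that it includes a cluster-by-time random effect and uses 18 between-cluster df. Do not require the term for Aim 2c, which has no baseline and is a single outcome over 18 months. State its reference distribution: under kappa 0, t(18) gives 2.9% where z gives 4.2%.
2. **GEE.** Use a bias-corrected sandwich (for example Kauermann-Carroll) with t(18), or F(2,17) if the test is joint.
3. **Decision rules.** State alpha, sidedness, and whether the interaction is the month-18 contrast or a joint test. Name one model and one outcome for the O'Brien-Fleming rule, and say how it relates to the primary model at the final look. If the corrected GEE is used for stopping, use t(8) with 5 clusters per arm at the interim, and state that it targets a population-average odds ratio. The mixed model with 8 df is very strict at the interim (0.00-0.20% against 0.52%).
4. **Power.** Simulate error and power for the test actually planned, over a stated range of baseline use and autocorrelation.

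**Cost.** No added clusters or visits. Items 1 and 2 are SAP wording and software options. Item 3 is more than wording, because it fixes the model, and possibly the estimand, behind stopping. In the mixed model, month-18 power falls by about 2-3 points, to about 80% for Aim 2a. The corrected GEE loses about 7-9 points on the time-by-arm contrast. The mixed-model test becomes somewhat conservative where clustering is low.
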